4.1 Hypothesis

This study has four specific objectives, with hypotheses associated with each objective. Understanding the study design will provide context for interpreting the hypotheses. Parent-child dyads will be randomized to one of two study arms. All dyads will receive the full Parents and Infants Engaged (PIE) intervention, but they will be coached on the two PIE domains (prelinguistic communication and sensory reactivity) in different orders. In Arm1, parents will first be coached in responding to their infants' prelinguistic communication cues. In Arm2, parents will first be coached on responding to their infants' prelinguistic communication cues. Posttest-1 assessments will follow the first domain of coaching for all participants. Then parents will be coached in the second domain of PIE, after which dyads will participate in Posttest-2 assessments.

1. Estimate the separate and combined effects of the two PIE intervention domains on dyadic engagement (primary outcome).
 - *H1a:* At Posttest-1, dyads coached in either PIE domain will exhibit moderately more dyadic engagement compared to Baseline (Cohen's $d \geq .40$).
 - *H1b:* At Posttest-2, dyads in both study arms will show additional small to moderate increases in dyadic engagement compared to Posttest-1 (Cohen's $d \geq .25$).
2. Estimate the separate and combined effects of the two PIE intervention domains on infant intentional communication.
 - *H2a:* At Posttest-1, infants in both groups will show no more than modest gains in

- intentional communication (Cohen's $d < .25$).
- *H2b*: At Posttest-2, infants in both groups will show moderate increases in intentional communication compared to Baseline (Cohen's $d \geq .40$).

3. Evaluate the *differential* changes in parent responsiveness following coaching on two individual Parents and Infants Engaged (PIE) intervention domains — responses to variable infant (a) sensory reactivity or (b) prelinguistic communication — as well as *cumulative* changes in parent responsiveness following coaching on both PIE domains.

- *H3a*: At Posttest-1, parents in both intervention arm will show increases in responses attuned to their infants' behaviors compared to Baseline, with parents coached in the sensory reactivity domain showing more responses attuned to infants' sensory reactivity, and parents coached in the prelinguistic communication domain showing more responses attuned to infants' signals of attention focus and communicative intent.

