5.1 General Design Description

This intervention trial will use a randomized comparative trial design. We will recruit participants by mailing the First Years Inventory v3.1 (FYIv3.1) to families of 11- 16-month-old infants based on public birth records for our catchment area (as in our prior studies), as well as distributing hard copies and links to an online version of the FYIv3.1 through area pediatric practices and public health clinics. Project staff will contact parents of infants who score at or above the threshold indicating an elevated likelihood of a future neurodevelopmental disorder (ND) diagnosis by phone to share the screening results and further screen for study exclusion criteria. If no exclusionary factors are identified, families will be informed about the overall study and specifically the baseline assessment. Families who provide consent for the baseline assessment will be assessed at our research offices, which include a child-friendly assessment suite. Final study eligibility will be determined by the baseline assessments (i.e., the infant must demonstrate receptive and/or expressive language scores one SD below the mean and meet clinically determined criteria suggesting extreme hypo- and/or hyper-reactivity). Parents of eligible infants will then be asked to consent to enrollment in the intervention trial. The project methodologist will randomize families of eligible infants (stratified for age < 14 months and \geq 14 months) to be initially coached on either the prelinguistic communication domain (Arm1) or the sensory reactivity domain (Arm2) of PIE. Families will participate in 6 weekly in-home coaching sessions in their respective treatment arms before returning to our research offices for Posttest-1 assessments. After Posttest-1, Arm1 dyads will receive 6 weeks of coaching on the sensory reactivity domain, and Arm2 dyads will receive 6 weeks of coaching on the prelinguistic communication domain; coaching for each group will also include review of the respective content domain coached in Study Phase 1. Then families will return for Posttest-2.

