6.1 Intervention

6.1.1 Description of Intervention

Parents and Infants Engaged is a parent-mediated intervention intended to improve engagement in parent-child dyads that include infants or young toddlers at elevated likelihood of a future diagnosis of autism spectrum disorder (ASD) or other neurodevelopmental disorders (NDs). Parent-child engagement is defined as an observable pattern of mutual focus, active participation, and reciprocity within an interactive context. PIE targets parent responsiveness to enhance parent-child engagement during family routines, and ultimately improve children's social, language, self-regulation, and cognitive outcomes. Within Parents and Infants Engaged, a coach addresses two domains in which early signs of NDs are often seen: Sensory Reactivity and Regulation (SR) and Prelinguistic Communication (PC). In the SR domain, the aim is to help parents recognize the sensory experiences afforded to the child, identify behavioral cues of a child's sensory experience, understand how parent responses to these cues can promote the child's regulatory abilities and engagement, and then practice effective response strategies. Similarly, the PC domain aims to help parents recognize their child's prelinguistic communicative acts, identify cues that children are communicating *intentionally*, understand how parent responses can promote more intentional communication and dyadic engagement, and then practice effective response strategies. Coaching occurs within the home, across varied daily routines.

Families are coached in either the SR or PC domain for their first 6 sessions (randomly assigned for the purpose of this trial), and then are coached in the other domain for an additional 6 sessions. Step one for coaching in each domain is to facilitate parental awareness and interpretation of infant sensory regulatory/prelinguistic communication behaviors. The second step shifts to incorporate observation and reflection on parent

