6.4 Statistical Method

6.4.1 Statistical Design

The study is designed as a randomized comparative trial with two phases. For Study Phase 1, dyads will participate in baseline assessments; then eligible, consenting families will be randomized, stratifying by child age, to one of two treatment arms. Arm1 families will participate in initial coaching on the PIE sensory reactivity (SR) domain, and Arm2 families will participate in initial coaching on the PIE prelinguistic communication (PC) domain. Families will participate in 6 weekly coaching sessions in their respective treatment arms, and return for Posttest-1. For Study Phase 2, dyads in Arm1 will receive 6 weekly coaching sessions on the PC domain, and dyads in Arm2 will receive 6 weekly coaching sessions on the SR domain. Then families will return for Posttest-2.

Comparisons of dyads assigned to Arm1 and Arm2 at Posttest-1 will allow us to estimate the separate effects of the two domains of PIE coaching, as dyads will have only been coached in one domain (responding to prelinguistic communication cues or sensory reactivity cues) prior to Posttest-1. At Posttest-2, we will get estimates of the additive effects of coaching in the second PIE domain, and be able to evaluate whether there are any effects of the order of coaching by comparing dyads in Arm1 to those in Arm2.

For analyses, we will utilize repeated measure analyses within a mixed modeling framework, to assess time and tx order effects, while accommodating missing data and optimally utilizing all available data.

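### Section 6.4.1 promises the additive effect of the second PIE domain at Posttest-2, but for dyadic engagement the design gives only the combined result of second-domain content, six more sessions and elapsed time

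*Combined protocol and SAP*

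**What the plan says.** Section 6.4.1 (Statistical Design) gives the claim: "At Posttest-2, we will get estimates of the additive effects of coaching in the second PIE domain". The same sentence goes on to a separate question, order effects, to be answered by comparing the arms.

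The delivery of coaching is described consistently:

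- 6.4.1, Phase 1: "Families will participate in 6 weekly coaching sessions in their respective treatment arms, and return for Posttest-1".
- 6.4.1, Phase 2, for one arm, with the other mirroring it: "dyads in Arm1 will receive 6 weekly coaching sessions on the PC domain".
- 6.1.1: "Families are coached in either the SR or PC domain for their first 6 sessions", "and then are coached in the other domain for an additional 6 sessions".
- 4.1: "All dyads will receive the full Parents and Infants Engaged (PIE) intervention". The arms differ only in order.
- 5.1, on Phase 2: "coaching for each group will also include review of the respective content domain coached in Study Phase 1".

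H1b, in 4.1 and again in 6.4.3.1, predicts that "dyads in both study arms will show additional small to moderate increases in dyadic engagement compared to Posttest-1", with d of at least .25. Section 6.4.3 makes the separate and combined effects of the two domains on dyadic engagement the primary objective. Section 6.4.2 says that the effect sizes will help to plan a larger efficacy trial. Section 6.2.1 says that evaluating efficacy is not an aim and that the controls for it are absent.

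**The concern.** The sentence in 6.4.1 names a quantity, the added effect of coaching in the second domain, and says that the trial will estimate it. To do so, the trial would need some dyads whose Phase 2 differs from the others in second-domain content but not in amount of coaching or time. There are none. At Posttest-1 every dyad has had six sessions. At Posttest-2 every dyad has had twelve, has met both domains, and has an infant who is at least about six weeks older.

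Dyadic engagement belongs to neither domain, so the outcome itself does not help to attribute the change. What is at stake is the label on a primary-objective estimate. If the Phase 2 change is passed to the efficacy trial as the contribution of the second domain, that trial would be planned on a quantity that this one did not measure.

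**Working it through.** **The plan's own figures.** The detectable effects in 6.4.2 were checked first, with N = 40, alpha .05, power .80, correlation ρ from .3 to .7, and m time points. The noncentrality is f²·N·m/(1+(m−1)ρ) between arms and f²·N·m/(1−ρ) for time and time-by-arm. With m = 2 this gives f = .366 to .419 between arms (plan: .37 to .42) and .269 to .176 within (plan: .27 to .18). The figures reproduce on two time points. They do not bear on this point, which concerns what can be estimated and not how precisely.

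**Mean gains by sequence and phase.** I use the order of domains and not the arm number, because the arm labels conflict. Arm 1 starts with sensory reactivity (SR) in the synopsis and 6.4.1 and with prelinguistic communication (PC) in 5.1 and 6.1.2, while 4.1 gives PC first for both arms. These passages must be reconciled, but the result below does not depend on which is right.

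Let m1, m2 be change due to time in each phase; g1, g2 the effect of six sessions of any coaching; sSR, sPC the specific effect of a domain coached first; and aSR, aPC that of a domain coached second.

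| Sequence | Baseline to Posttest-1 | Posttest-1 to Posttest-2 |
|---|---|---|
| SR then PC | m1 + g1 + sSR | m2 + g2 + aPC |
| PC then SR | m1 + g1 + sPC | m2 + g2 + aSR |

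There are four observable mean gains and eight components, and the rank is 4. A rank check gives:

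- aPC: not estimable.
- aSR: not estimable.
- Their average: not estimable.
- aPC − aSR: estimable, from the between-arm difference in Phase 2 gain.
- m2 + g2 + aPC, and likewise m2 + g2 + aSR: estimable as a total for each arm.

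The reason can be seen directly. Add any constant k to both aPC and aSR and subtract k from g2. All four means stay the same, so no data from this design can distinguish k = 0 from any other value.

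**Setting maturation to zero does not help.** With m2 = 0 the Phase 2 gains are g2 + aPC and g2 + aSR, and the same shift by k applies.

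**The Phase 2 review of the first domain.** Write rSR and rPC for its effects. The Phase 2 gains become m2 + g2 + aPC + rSR and m2 + g2 + aSR + rPC. Their difference is (aPC − aSR) + (rSR − rPC). The between-arm difference is still estimable, but it compares two Phase 2 packages and not two pure domain effects.

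**What would identify the effect.** If arms that stayed in one domain existed, their Phase 2 gain would be m2 + g2, and switch minus stay would give aPC or aSR, assuming equal time and general-coaching effects. For scale only, suppose that difference were d = .25 (H1b's value, borrowed as an assumption), at two-sided .05 and 80% power, with SD of change √(2(1−ρ)). Then n per arm = 2(1.96 + 0.84)²·2(1−ρ)/.25²:

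| ρ | n per arm | Power with 20 per arm |
|---|---|---|
| .3 | 352 | 10% |
| .5 | 252 | 12% |
| .7 | 151 | 17% |

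Adding such arms is not realistic for a study of 44 dyads. The remedy therefore lies in the wording.

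**The case against.** The best defence is that *additive* need mean no more than the increment from the second block as delivered. H1b itself predicts only a further rise and does not say whether content or dose causes it. This has some force: the text is open to that reading. But the sentence credits the increment to coaching in the second domain, and even the increment of the block as delivered is mixed with maturation, since no dyads go uncoached.

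Second, 6.2.1 disclaims efficacy, and 6.4.2 ranks description above testing. This lowers the stakes. It does not correct a specific statement in the statistical section about what will be estimated.

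Third, 6.4.3 allows a post hoc covariate for number of sessions. Session counts are not randomised, and every Phase 2 session is by design a second-domain session, so the covariate cannot separate the two.

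A reader might go further than the documents allow in four ways.

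- One might divide H1b's .25 by H1a's .40 and say that same-domain continuation need deliver only 63% of the first-phase gain for H1b to be met. Both values are hypothesis thresholds, and nothing in the plan says what continuation would deliver, so the ratio is not evidence.
- One might expect a general coaching effect to cancel when the gain on one responsiveness rating is set against the gain on the other. The two project-developed 1–7 ratings have no stated common metric. The previously coached rating may be near its ceiling, and the Phase 2 review also acts on it.
- One might infer that a met H1b will be reported as proof that the second domain adds value beyond dose. The plan does not say so.
- One might conclude that Posttest-2 tells nothing about domains. That is too strong: the randomised between-arm difference is estimable, and Objective 3 already examines domain-specific parent responsiveness.

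**Conclusion.** The sentence in 6.4.1 is wrong as written: it states an estimand that the design does not deliver. For dyadic engagement, the Posttest-1 to Posttest-2 change is the sum of second-domain content, with review of the first domain, six further sessions and elapsed time. Neither second-domain effect, nor their average, can be separated out. Only the between-arm difference in that change can be attributed to anything narrower, and it reflects the whole Phase 2 package.

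This rests on the delivery described in 4.1, 5.1, 6.1.1 and 6.4.1, and on no assumption about effect sizes, correlation or maturation. The distortion has no numerical size, because the documents give nothing with which to divide the total. Severity is modest: the planned analyses remain usable, and 6.2.1 already limits causal claims in general terms. What changes is the conclusion from H1b and the meaning of the effect sizes handed to the next trial.

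**What to change.** In 6.4.1, replace the sentence with: *the Posttest-1 to Posttest-2 change describes further change over a second block of six sessions in the other domain (content, additional coaching and time combined); it does not isolate the effect of the second domain.* Keep the clause on order effects. Apply the same limit to the H1b conclusion in 4.1 and 6.4.3.1, and to the effect sizes in 6.4.2 that will inform the efficacy trial. While editing 6.4.3.1, name the Posttest-1 to Posttest-2 contrast that H1b needs, since only contrasts from Baseline are listed.

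Optionally, as supportive evidence on parent responsiveness only, compare the Phase 2 gain between arms within each rating: on the SR rating, dyads newly coached in SR against those coached in it earlier, and likewise for PC. This keeps one metric per comparison and makes explicit a contrast close to Objective 3. It assumes equal general coaching and time effects across arms. Ceiling effects and the Phase 2 review should be stated as caveats. It says nothing about dyadic engagement, so the rewording is needed either way.

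The cost is a few sentences and, if wanted, one contrast on ratings already collected at all three time points. The claim for the second domain becomes weaker.

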6.4.2 Sample Size Considerations

Assuming recruitment of 44 infant-parent dyads and allowing for a 9% (n=4) dropout rate, which is consistent with high retention rates (> 95%) in our prior intervention studies, 40 dyads (20 per treatment arm) will have complete data for analyses. Assuming a conventional type I error rate of .05, and intercorrelations among the repeated measures from .3 to .7, the magnitude of treatment group effects detectable with a .80 statistical power will range from $f=.37$ to $.42$, respectively, which are large standardized effects. The magnitude of time effects and time-by-treatment arm interaction effects detectable with a .80 power will range from $.27$ to $.18$, also respectively, which are medium-sized standardized effects. Thus, the study is underpowered to detect any but large differences

between the treatment arms and medium-sized or larger effects on time and time-by-treatment arm interactions. More important than the statistical comparisons, though, the analyses will yield key descriptive characterizations of the treatment-arm effects at the two posttest points (i.e., means, medians, proportions, and variances) on key outcomes, as well as effect size estimates that can be used in planning a larger scaled efficacy trial of the PIE intervention.

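### The .80 power given for treatment-arm effects in 6.4.2 belongs to an arm difference averaged over two occasions, not to the single-posttest arm comparisons planned in 6.4.1

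*Combined protocol and SAP*

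**What the plan says.** Section 6.4.2 (Sample Size Considerations) expects 40 of 44 dyads, 20 per arm, to have complete data. Its other inputs are "Assuming a conventional type I error rate of .05" and "intercorrelations among the repeated measures from .3 to .7". For the arms it reports that "the magnitude of treatment group effects detectable with a .80 statistical power will range from $f=.37$ to $.42$, respectively, which are large standardized effects". The next sentence deals with the other two model terms: "The magnitude of time effects and time-by-treatment arm interaction effects detectable with a .80 power will range from $.27$ to $.18". The section names neither a formula nor the number of occasions behind these figures.

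Section 6.4.1 (Statistical Design) sets out the arm comparisons. For the first posttest: "Comparisons of dyads assigned to Arm1 and Arm2 at Posttest-1 will allow us to estimate the separate effects of the two domains of PIE coaching". For Posttest-2, the investigators expect to "be able to evaluate whether there are any effects of the order of coaching by comparing dyads in Arm1 to those in Arm2".

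Section 6.4.3.1 puts arm, time and arm-by-time terms in the model. It reads the arm term as a difference between arms on the outcome, and the interaction as unequal change from Baseline. Section 6.4.4 runs the models without covariates first.

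**The concern.** The treatment-group figure rises with the correlation, from .37 to .42. An arm comparison at one visit without baseline adjustment does not depend on the correlation between visits at all. The printed figure therefore cannot be the power of the comparisons described in 6.4.1; it must belong to something averaged over visits.

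An averaged arm effect assumes the same arm difference at each occasion. This design does not produce that naturally. At Baseline the arms are equal in expectation through randomisation. At Posttest-1 each arm has had a different single domain, and at Posttest-2 both arms have had both. For parent responsiveness, H3a predicts arm differences at Posttest-1 and H3b predicts none at Posttest-2.

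At stake is how a null arm or order result is read. Someone relying on 6.4.2 would think that a single-posttest comparison had an 80% chance of detecting f=.37 to .42. For H3b, where no arm difference is the predicted result, that overstates what a null finding shows.

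**Working it through.** **Inputs from 6.4.2.** N=40 (20 per arm), alpha .05 (taken as two-sided), power .80, correlation ρ = .3 and .7. For two equal arms, d = 2f. The number of occasions m is not stated, so it was varied.

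**1. Reproducing the printed figures.** The arm main effect in a repeated-measures analysis has noncentrality λ = f²·N·m / (1 + (m−1)ρ), on 1 and 38 df. Power of .80 on those df needs λ = 8.266.

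- m=2, ρ=.3: f = √(8.266 × 1.3 / 80) = .3665, printed as .37.
- m=2, ρ=.7: f = √(8.266 × 1.7 / 80) = .4191, printed as .42.

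For the time and interaction terms, λ = f²·N·m / (1−ρ), also on 1 and 38 df when m=2.

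- ρ=.3: f = √(8.266 × .7 / 80) = .2689, printed as .27.
- ρ=.7: f = √(8.266 × .3 / 80) = .1761, printed as .18.

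All four figures match at m=2. Three occasions give .332 and .407 for the arm effect and .242 and .158 for the others. Using 44 dyads, or alpha .10, also fails to reproduce the set.

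**2. The comparison in 6.4.1: arms at one posttest, unadjusted (m=1).** Here λ = f²·N.

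- f=.37: λ = .1369 × 40 = 5.48, power 62.6%.
- f=.42: λ = .1764 × 40 = 7.06, power 73.5%.
- Detectable with .80 power: f = √(8.266 / 40) = .4546, so d = .91, at any ρ.

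Rounding of the printed f moves the powers only to 61–64% and 73–75%. With all 44 dyads they would be 66.9% and 77.7%.

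**3. The averaged term when the arms differ only at the posttest and the other occasion is Baseline.** The averaged effect is f/2.

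- ρ=.3: λ = .185² × 80 / 1.3 = 2.11, power 29.3%.
- ρ=.7: λ = .21² × 80 / 1.7 = 2.08, power 29.0%.

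**4. Arm difference in change from Baseline.** For a posttest difference f and none at Baseline, λ = f²·N / (2(1−ρ)). Setting this equal to the interaction formula with m=2 gives posttest f = 2 × interaction f. The unrounded interaction values therefore convert to 2 × .2689 = .54 (d=1.08) at ρ=.3 and 2 × .1761 = .35 (d=.70) at ρ=.7. The printed interaction figures already carry this information.

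At the stated arm effects, this contrast has λ = .1369 × 40 / 1.4 = 3.91 (power 49%) at f=.37, ρ=.3, and λ = .1764 × 40 / .6 = 11.76 (power 92%) at f=.42, ρ=.7.

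**5. Baseline-adjusted contrast, for reference.** λ = f²·N / (1−ρ²), on 1 and 37 df. Power is 67% at f=.37, ρ=.3 and 95% at f=.42, ρ=.7. The detectable effect is f=.43 to .32.

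**The case against.** The strongest reply is that the figure is right for a term the model contains. Section 6.4.3.1 includes an arm term and interprets it on its own. Section 6.4.3.2 does the same for Objective 4, whose outcomes are analysed at exactly two occasions, Baseline and Posttest-2. This stands. A reader might infer an arithmetic error, or that no arm term of this form is planned, and the documents support neither. What remains is that 6.4.1 describes separate comparisons at each posttest, and the averaged term is weak for a difference that arises only after Baseline.

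Second, arm contrasts that use Baseline are powered in the next sentence of 6.4.2, through the interaction. This also stands. A reader might see .37 to .42 and conclude that the plan has the effect of correlation backwards. It does not. Detectable averaged arm effects do grow with correlation, and the interaction figures fall from .27 to .18, as they should.

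Third, the mixed model uses all available data, so a posttest-only calculation may look too pessimistic. With complete data, a full arm-by-time model and no constraint or adjustment at Baseline, the estimated arm difference at one posttest is simply the difference in means there, so step 2 applies. But 63% and 74% should not be read as a shortfall in every arm contrast. At a correlation of .7, the change and adjusted contrasts exceed 80% at the stated effect.

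Fourth, 6.4.2 admits low power for arm differences and puts description and effect-size estimation ahead of testing, and 6.2.1 disclaims efficacy aims. This limits the consequence but does not correct the number, because the section calls .37 to .42 large and says that large arm differences are within reach.

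**Conclusion.** The point holds and is minor. The stated .80 power is attached to the wrong contrast. It is correct for an arm difference present equally at two occasions, but the arm comparisons at Posttest-1 and at Posttest-2 have about 63% power at f=.37 and 74% at f=.42, and need f=.45 (d=.91) to reach 80%.

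This assumes 20 dyads per arm with complete data, equal standard deviations, a two-sided test at .05 and no baseline adjustment. The two-occasion formula is inferred from its match to all four printed figures, since the protocol does not name it.

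The conclusion that only large arm effects are detectable survives, and so does the sample size. The primary hypotheses H1a and H1b concern change over time, and their power figures are unaffected.

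**What to change.** In 6.4.2, state that f=.37 to .42 applies only to an arm difference present equally at both of two occasions. Then add:

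> With 20 dyads per arm, the arm difference at Posttest-1 or at Posttest-2 detectable with .80 power is f=.45 (d=.91) without baseline adjustment; as a difference in change from Baseline it is f=.54 to .35 (d=1.08 to .70) at correlations of .3 to .7.

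Leave the time and interaction figures as they are. Give the baseline-adjusted range (f=.43 to .32) only if that adjustment becomes a planned analysis, because 6.4.4 makes covariates a conditional second step.

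The cost is a clarification and one added sentence, and a somewhat less favourable stated detectable effect. Enrolment, visits and data collection do not change.

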6.2 Assessments

6.2.1 Efficacy

The aims of the current proof-of-concept trial do not include an evaluation of the efficacy of the PIE intervention, and the design of the study does not include the necessary controls for an efficacy evaluation. The timing and procedures for assessments and the rationale for selecting them within the context of our study aims have been described elsewhere in this protocol (5.2.1 Primary outcome variables; 5.2.2 Secondary and Exploratory variable; 6.1.3

Selection of Instruments/Outcome Measures; Visit Schedule Table; Study Flow Chart).

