Although we are performing multiple statistical tests across outcomes and hypotheses in addressing the three specific aims, in this project is more important to avoid overlooking statistical signals of effectiveness of the novel intervention approach (type II errors), than avoiding false assertions of effectiveness (type I errors). We believe it is premature, therefore, to employ conservative adjustments to the type I error rates in statistical tests, which would compromise the power of statistical tests to detect such signals.

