6.4.3.1 Primary Analyses

The primary objective of this study is to examine whether the novel PIE intervention transforms parent-infant transactions over time as intended, thereby facilitating increases in the time infants spend in dyadic engagement with their parents. We will also evaluate whether dyadic engagement outcomes differ based on whether parents are coached first in the sensory reactivity domain followed by coaching in the prelinguistic communication domain, or are coached in the opposite order.

Specifically, we will estimate the separate and combined effects of the two PIE intervention domains on dyadic engagement (primary outcome). H1a: At Posttest-1, dyads coached in either PIE domain will exhibit moderately more dyadic engagement compared to Baseline (Cohen's $d \geq .40$). H1b: At Posttest-2, dyads in both study arms will show additional small to moderate increases in dyadic engagement compared to Posttest-1 (Cohen's $d \geq .25$).

Our primary analysis will be conducted to explore a priori contrasts of interest within using repeated measures within a mixed modeling framework. Of key interest will be the contrast of Baseline to Posttest-1 scores and the contrast of Baseline to Posttest-2 scores (time effect). In addition, the model will include terms for treatment arm effects and treatment arm-by-time interactions. A time effect will indicate growth in the outcome from baseline to the posttest point, a zero or negligible time effect indicates stability, and a negative time effect suggests a drop in scores. A non-negligible treatment arm effect indicates that the two treatment arms differ on the outcome; while a non-negligible interaction coefficient suggests that the magnitude of change from baseline to the posttest point are not equivalent for members of the 2 treatment arms. Since the primary outcomes are proportions, arc sin transformations of these proportions will be performed before entering them into the models.

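### Baseline-to-posttest change includes ordinary infant development, so it cannot estimate the combined effect of PIE or supply the assumed effect for an efficacy trial

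*Combined protocol and SAP*

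**What the plan says.** - Section 4.1: dyads are randomised to the order of the two coaching domains, and all of them receive the full intervention. No group goes without PIE.
- Section 6.4.3.1: "we will estimate the separate and combined effects of the two PIE intervention domains on dyadic engagement". H1a is a pre-post d of at least .40 at Posttest-1. H1b is a further d of at least .25 from Posttest-1 to Posttest-2. The contrasts given priority are Baseline to Posttest-1 and Baseline to Posttest-2. Arm and arm-by-time terms are also in the model.
- Section 6.4.3, when declining multiplicity adjustment, says that the priority is not to miss "statistical signals of effectiveness of the novel intervention approach".
- Section 6.4.2 offers "effect size estimates that can be used in planning a larger scaled efficacy trial of the PIE intervention". Sections 3.2 and 3.3.2 likewise send the estimated effect sizes to a larger efficacy trial.
- Section 6.2.1: the aims exclude an efficacy evaluation, and "the design of the study does not include the necessary controls for an efficacy evaluation".
- Section 6.4.4: models are first run without covariates. Covariates are considered only if a baseline characteristic differs between arms.

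**The concern.** Randomisation here separates one domain from the other at Posttest-1 and one order from the other at Posttest-2. It does not separate PIE from the passage of time. Infants enter at 11 to 16 months and are followed for at least 16 weeks from baseline. Section 5.3.2 itself describes the first two years as a time of very active neural development, and families are encouraged to seek community services (section 6.3.2). All change from such sources stays in the time contrasts.

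The covariate rule in 6.4.4 does not address this. Growth common to both arms is not an imbalance between arms, and randomisation is stratified by age.

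Two things are at stake. H1a and H1b could be declared met with little or no PIE effect. A later controlled trial could also be sized on a pre-post d that is larger than the PIE-versus-control difference.

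**Working it through.** **1. The plan's own figures (6.4.2).** Inputs: "40 dyads (20 per treatment arm) will have complete data for analyses", after "allowing for a 9% (n=4) dropout rate" (44 − 4 = 40; 4/44 = 9.1%); "Assuming a conventional type I error rate of .05"; "intercorrelations among the repeated measures from .3 to .7"; power .80. For N dyads in two groups, m occasions and correlation ρ, the noncentrality is:
- between arms: λ = f²Nm / [1 + (m − 1)ρ], with df 1 and N − 2;
- time and time-by-arm: λ = f²Nm / (1 − ρ), with df m − 1 and (N − 2)(m − 1).

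With N = 40 and m = 2, the detectable f at ρ = .3 and .7 is .366 and .419 between arms, and .269 and .176 for time. The plan states .37 to .42 and .27 to .18, so its figures reproduce. They correspond to two occasions, although the primary outcome has three; with m = 3 the values are .332/.407 and .242/.158. These figures say how large a time change can be detected. They do not say what caused it.

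**2. What each contrast contains.** Let G be the growth common to both arms up to a visit, and P1 and P2 the PIE effects in the two arms at that visit.
- Time contrast, averaged over arms: G + (P1 + P2)/2.
- Between-arm contrast: P1 − P2. G cancels.

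No planned contrast isolates (P1 + P2)/2, which is the combined effect.

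**3. Elapsed time.** Sections 6.3.1 and 6.3.5 give at least 16 weeks from baseline to Posttest-2, and an average of about 22 to 25 weeks from screening to Posttest-2. I take 8 weeks to Posttest-1 (introductory visit, six weekly sessions, assessment), or 11 if visits slip. At 4.345 weeks per month these are 1.84 and 2.53 months.

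**4. Growth that would meet the thresholds with no PIE effect** (d on the baseline SD; the plan does not define the SD for d):
- H1a: .40/1.84 = 0.22 SD per month at 8 weeks; .40/2.53 = 0.16 at 11 weeks.
- H1b, with the same interval for the second phase: .25/1.84 = 0.14; .25/2.53 = 0.10.

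**5. Chance of an observed d of at least .40 at Posttest-1 with no PIE effect** (simulation, 40 dyads pooled over arms, 20,000 runs; ρ = .3 / .7):

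| Assumed growth, SD per month | 8 weeks | 11 weeks |
|---|---|---|
| 0.10 | 13% / 5% | 23% / 14% |
| 0.20 | 44% / 41% | 71% / 80% |
| 0.30 | 79% / 88% | 97% / >99% |

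**6. Planning consequence.** For two arms, 80% power and two-sided .05, n per arm = 2(1.96 + 0.84)²/d², about 15.7/d². At d = .40 this is 99 per arm.

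| Part of d = .40 that is growth | Net d | Power with 99 per arm | n per arm needed |
|---|---|---|---|
| 0 | .40 | 80% | 99 |
| .10 | .30 | 56% | 175 |
| .20 | .20 | 29% | 393 |
| .30 | .10 | 10% | 1570 |

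**7. Would adjusting for age at visit cure it?** Within an infant, age and time are almost collinear, so the adjustment relies mainly on the age slope between infants. Simulation with no PIE effect (44 dyads, ages 11 to 17 months, visits 8 to 12 weeks apart, correlation .5, within-infant growth .18 SD per month) leaves these time d values at Posttest-1 / Posttest-2:
- between-infant slope equal to within-infant growth: about 0 / 0;
- half of it: .20 / .40;
- zero: about .40 / .80;
- 1.5 times it: −.18 / −.36.

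In simulation with equal slopes, the SE rises from about .15 unadjusted to about .22 and .35. At Posttest-2 the 95% half-width is then 1.96 × .35 = .69.

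**The case against.** The strongest reply is that the plan already discloses the limitation. Section 6.2.1 disclaims efficacy, the study is called proof of concept throughout, 6.4.2 ranks description above testing, and 6.4.3.1 explains a time effect neutrally as growth in the outcome. This stands as context. It does not cure the planning use: a design that lacks efficacy controls cannot supply an efficacy trial's assumed effect, and the disclaimer is not carried into section 6.4.

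The wording also needs a fair reading.
- Section 6.4.1 ties the separate effects of the domains to randomised comparisons of the arms at Posttest-1, where common growth cancels. A reader might infer that everything under Objective 1 is contaminated. The documents do not support that; the problem lies in the combined effect and in H1a/H1b.
- The sentence in 6.4.2 also mentions treatment-arm effects, and it does not say that the effect sizes are pre-post d values. That they include pre-post d is an inference, though a reasonable one given H1a, H1b and section 3.2.
- The remark in 6.4.3 about signals of effectiveness covers all tests, not the time contrasts in particular.

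Finally, the infants are selected for language delay and atypical sensory reactivity, so strong spontaneous growth in reciprocal engagement cannot be presumed. That also stands, and it is why every figure on growth is conditional.

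**Conclusion.** The point holds. The time contrasts and H1a/H1b measure PIE plus development, and cannot estimate the combined effect of PIE or provide the assumed effect for an efficacy trial. This follows from the design and needs no assumption about growth.

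The size of the bias is unknown. Growth of 0.16 to 0.22 SD per month reaching d = .40, and 29% power if half of .40 is growth, are illustrations. They rest on the assumed 8 to 11 weeks to Posttest-1 and on d scaled by the baseline SD.

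Three stronger readings are tempting and not supported.
- That growth will meet H1a, or that a later trial will be underpowered: the documents give no growth rate, and at 0.10 SD per month the chance of meeting H1a on growth alone is 5% to 23%.
- That adjusting for age removes the bias: it does so only if the between-infant age slope equals within-infant growth, and selection on language and sensory cut-offs may break that.
- That the between-arm contrasts can size the efficacy trial instead: they compare PIE with PIE, so they inform only domain or order questions.

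**What to change.** - **6.4.3.1:** describe the time contrasts and H1a/H1b as uncontrolled *change during PIE, including development*. Keep *effect* for the randomised between-arm contrasts (domain at Posttest-1, order at Posttest-2).
- **6.4.2, 3.2 and 3.3.2:** limit what is carried into efficacy-trial planning to SDs, repeated-measures correlations and retention. State that pre-post d will not be used as the assumed PIE-versus-control effect, and that between-arm contrasts inform only domain or order questions.
- **Optional:** report a model with age at visit, labelled as a sensitivity analysis. State its equal-slope assumption, why selection may break it, and its imprecision.

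The cost is wording and a more modest headline claim, plus one extra model per outcome if the option is taken. No control arm is needed.
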